#### 13.4 PARTICIPANT AND DATA CONFIDENTIALITY

Each Investigator must assure that the privacy and confidentiality of each study patient's personal identity and personal medical information is maintained at all times. In order to maintain subject privacy and confidentiality, all CRFs, laboratory specimens, evaluation forms, reports, and other records, documents and image material that leave the site will be identified only by an identification code. This identification code shall on no occasion include study subject's names, initials or date of birth.

Medical information release or review of the personal health data of study patients shall take place solely within regulated and approved circumstances, and only to third parties, specifically identified by the written informed consent document signed by the study patients, except as permitted by applicable laws and regulations for purposes of monitoring and data verification by the relevant regulatory authorities, the NIH and NIH's properly authorized representatives, or other regulatory authorities. Personal medical information will always be treated as confidential.

### 14 DATA HANDLING AND RECORD KEEPING

#### 14.1 DATA COLLECTION AND MANAGEMENT RESPONSIBILITIES

Each Investigator must keep a separate patient identification list showing code numbers, names, and dates of birth to allow unambiguous identification of each patient included in the study. A note will be made in the medical records that the patient is participating in a clinical study.

All required data will be recorded on the CRF by study center personnel according to the data entry guidelines provided by the PI or designee. All CRFs must be kept in good order and updated so they always reflect the latest observations on the patients participating in the study.

When paper CRFs are used, they will be completed legibly in black ink, with reasons given for missing data. Any corrections to the data will be made in a manner that does not obscure the original entry and will be dated and initialed by the Investigator or assigned designee. Each Investigator will sign the statement on the last page of the CRF.

When eCRFs are used, electronic signatures of the Investigator (or designee) will be provided.

Access to the eCRF for data entry and signature is controlled by user identification and password, which are provided by the PI or designee. Study center personnel will be trained, by the PI or designee, in the use of eCRFs and application of electronic signatures before the start of the study.

Because it is extremely important to have proper data collection in a timely manner, the Investigator shall complete the CRFs and on an ongoing basis. If a study monitor is needed and study monitor requests additional data or clarification of data for the CRF, the request must be answered satisfactorily in a timely manner before the next monitoring visit.

#### 14.2 STUDY RECORDS RETENTION

All records related to the study (i.e., source data, source documents, CRFs, copies of protocols and protocol amendments, correspondence, patient identification lists, signed informed consent forms, and other essential documents) must be retained for a minimum of 5 years.

Should an Investigator wish to assign the study records to another party or move them to another location, advance written notice will be given to the PI and NIH.

The Investigator will maintain all study records according to International Conference on Harmonization (ICH)-GCP and applicable regulatory requirements. Records will be retained for two (2) years following the date a marketing application is approved for the indication pertaining to this clinical study; or, if the medication is planned to be terminated or if a Regulatory application is not planned to be progressed, until two (2) years after the investigation is discontinued and the Food and Drug Administration (FDA), or competent regulatory authority, is notified.

### 14.3 PROTOCOL DEVIATIONS

A **protocol deviation** is non-adherence to protocol-specific study procedures or schedules that does not involve inclusion/exclusion criteria, primary objective variable criteria, and/or GCP guidelines. Deviations are considered minor and do not impact the study.

A **protocol violation** is any significant divergence from the protocol, i.e., non-adherence on the part of the patient, the Investigator, or the sponsor to protocol-specific inclusion/exclusion criteria, primary objective variable criteria, and/or GCP guidelines. Protocol violations will be identified and recorded, by study center personnel.

No **exceptions** to protocol-specific entry criteria will be granted to allow patients to enter a study.

### 14.4 PUBLICATION AND DATA SHARING POLICY

#### **RESOURCE SHARING PLAN**

This includes the following activities:

- Publicizing the study as it is initiated, to trial investigators and other interested researchers
- Identifying and supporting proposals, (funding sources, implementation, analyses) for feasible salient ancillary studies;
- Providing a fully anonymized data set for future analyses/studies by interested researchers, once the trial funding has ended.

Each of these activities is discussed below.

#### **Publicizing the Study**

The key methods for publicizing the trial are:

- ClinicalTrials.gov – the government website that registers all initiated trials with trial protocol descriptions and contact information;
- The trial site PI's and involved leadership group
- Design and rationale paper will be submitted for publication
- A final manuscript will be submitted after conclusion of the study.

#### **Providing Access to Linked, Anonymized Data**

Once trial funding ends, two options will be:

- Provide the anonymized data set to NHLBI.
- Maintain the linked, anonymized data set via the IU Data Coordinating Center.

Regardless of which option is implemented, information on availability of data will be accessible on ClinicalTrials.gov and will be linked to other appropriate sites, including Indiana University websites.

#### **PREPARATION OF THE ANONYMIZED, LIMITED ACCESS DATASET**

To comply with NHLBI requirements for an adequately anonymized dataset, we propose the following activities for the data set:

1. Subject identifiers:
  - a. New random identification numbers without site identifiers will replace the original identification numbers, once data acquisition is complete.
  - b. The key linking the original and new ID numbers will NOT be provided to users of the anonymized data set, nor to site investigators and staff.
2. Variables that might lead to the identification of participants:
  - a. Interviewer or technician identification numbers or codes will be recoded or deleted.
  - b. Regional variables with little or no variation within a center because they could be used to identify the center will be deleted.
  - c. Unedited, verbatim responses that are stored as text data (e.g., specified in “other” category) will be deleted.
3. Dates: All dates will be coded relative to a specific reference point (e.g., date of randomization). This provides privacy protection for individuals known to be in a study who are known to have had some significant event (e.g., myocardial infarction) on a particular date. Birth and other milestone dates will also be recoded relative to a specific reference date.
4. Variables with low frequencies for some values, that might be used to identify participants, may be recoded. These might include:
  - a. Socioeconomic and demographic data (e.g., marital status, occupation, income, education, language, number of years married).
  - b. Household and family composition (e.g., number in household, number of siblings or children, ages of children or step-children, number of brothers and sisters, relationships, spouse in study).
  - c. Numbers of pregnancies, births, or multiple children within a birth.
  - d. Anthropometry measures (e.g., height, weight, waist girth, hip girth, body mass index).
  - e. Physical characteristics that are distinctive (e.g., blindness).
  - f. Prior medical conditions with low frequency (e.g., group specific cancers into broader categories) and related questions such as age at diagnosis and current status.
5. Race/ethnicity and gender information when very few subjects are in certain groups or cells.
  - a. Polychotomous variables: values or groups will be collapsed so as to ensure a minimum number of subjects (e.g., at least 20) for each value within each race-gender cell.
  - b. Continuous variables: distributions will be truncated if needed to ensure that a minimum number of subjects (e.g., at least 20) have the same highest and lowest values in each race-gender cell.
  - c. Dichotomous variables: data should either be grouped with other related variables so as to ensure a minimum number of subjects (e.g., at least 20) in each race-gender cell or deleted.

## **CLINICAL TRIALS.GOV**

This study will be registered at the appropriate and required time by the PI, in conjunction with the DCC, to the government-operated clinical trial registry data bank, which contains registration, results, and other information about registered clinical trials at ClinicalTrials.gov. Federal law under FDAAA requires clinical trial information for certain

[figure not shown]
clinical trials to be submitted to the data bank and this study will comply with all reporting requirements for clinical trials.

## 16 CONFLICT OF INTEREST POLICY

All investigators must adhere to national, regional, and local conflict of interest policies. Prior to publication, all disclosures potentially relevant to this trial will be explicitly stated.

## 17 ADDITIONAL TRAINING MATERIALS

### 17.1 LUNG ULTRASOUND TRAINING OVERVIEW

#### Lung Ultrasound Training Overview

[figure not shown]
Each clinical site already has expertise in LUS (lung ultrasound). However, to minimize variation, a standardized teaching format will be utilized, emphasizing the 8 zone scoring system. Videos perform better to explain LUS and B-lines than a word document or PDF. Videos will be utilized for training purposes, however, a document representation is listed below.

Why use lung ultrasound? For all of the following reasons:

- a. It is fast
- b. No radiation
- c. Non invasive
- d. Repeatable

Ultrasound has been used at the bedside for years. Machines continue to get smaller and smaller and easier to move around.

What is the difference between focused ultrasound and formal echocardiography or radiology studies? Focused ultrasound does not replace formal echocardiography or formal radiology studies. It is meant to answer a binary clinical question. For the purpose of our study, it is meant to guide AHF management. [The figure below with red arrows shows examples of B-lines]

Lung (or pulmonary ultrasound) is one of the easiest ultrasound assessments to learn and perform. Even in patients with a high BMI, the lung can be evaluated. Additionally, lung ultrasound has high inter-rater agreement.

[figure not shown]
In this figure to the left, we are seeing B lines – vertical echogenic artifacts originating from the pleural line, extending to the bottom of the ultrasound screen and moving with lung sliding. In AHF patients, B-line assessment aids in diagnosis, prognosis and may guide

acute management.

Below is the curvilinear probe used for the images.

Below is a pictorial representation of the 8-zone scoring system.

[figure not shown]
The eight zone protocol breaks each hemi-thorax into 4 zones, divided by the parasternal (PS) Line, Ant axillary line (AAL), posterior axillary line (PAL) and anatomic nipple line (ANL). In the clinical setting of suspected AHF, pulmonary edema is determined sonographically as greater than three B-lines in a rib space in at least two lung zones bilaterally. For scoring purposes, a B line cut off of 10 has been described previously in the literature. This allows for a more precise quantification of pulmonary edema. B lines will be counted as the number seen per acoustic window.

#### Machine settings

- Enter patient data
- Select **curvilinear** probe
- Select thorax exam
- Set **depth** to 18 cm
- Set **clip length** to 6 seconds
- Turn off tissue harmonics and multi-beam former
- Adjust **gain** so that the rib shadow is black and pleural line is distinct

[figure not shown]
## Image acquisition

- Patient supine
- 45 degrees of bed elevation (as possible, if not possible please note on CRF)

[figure not shown]
- Starting off on the **Right** in **Zone 1**: you want the indicator towards the patient's head. Identify ribs by shadowing and identify a rib space (see image below)
- Label R1
- Then turn 90 degrees with **indicator towards patient's right** so you are still in a rib space but the probe is **HORIZONTAL**
- Scan within the zone until you see the area of most B lines
- Record 6 second clip (this should include both inspiration and expiration)
- Repeat the above for Right zones 2-4 and Left zones 1-4
- Obtain **VERTICAL** R4 and L4 zones
- 10 TOTAL videos
- After you leave the bedside, record the number of B lines on a standardized data collection form or in REDCap

## COUNTING B LINES

- B lines are vertical echogenic artifacts that originate from the pleural line and extend to the bottom of the ultrasound screen
- Below image is an example of how to count individual B lines

Figure 3: Counting of B-lines using Lung Ultrasound

- In the situation where the whole footprint is 'white out' (see below image) count as 20 B lines
- The maximum number of B lines per sector is 20
- Count the maximum number of B lines you see
- If half of the footprint is a 'white out' count as 10 B lines
- Estimate percentage of white out
- Count up and down from there

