#### Lung Ultrasound (LUS) Protocol

To best determine the potential value of EVLW measurements using LUS, we will assess patients at multiple timepoints throughout hospitalization. (See Figure 1 – Trial design flow below)

Figure 1: Trial Schematic

For diagnostic purposes, previously published protocols have been the most well-studied.

Each LUS scan consists of 8 sectors as seen in figure 2. (Figure reproduced from Volpicelli et.al.7) Trained research personnel will record and count B-lines in each sector as visualized through one respiratory cycle at each of the time points listed in the Figure. At minimum, each stored video clip will be 6 seconds in length. The total number of B-lines for all 8 sectors will comprise the overall score. With training, the entire scan takes less than 10 minutes.

As patient positioning may impact B-lines, patients will be placed at approximately 45 degrees for all scanning. The CRF will be marked if patients are unable to lie at this angle.

- An 8 zone LUS scan will be done at the following times:
  - T00: initial LUS scan (in ED for screening and eligibility)
  - T02: 2-4 hours after initial treatment (in ED) (+/- 30 minutes)
  - T06: 2-4 hours after T02 or pre-ED discharge, whichever comes first (+/- 60 minutes)
  - HD2: 24 hours after initial scan (Day 2) (+/- 6 hours)
  - HD3: 48 hours after initial scan (Day 3) (+/- 8 hours)
  - HD4: Day 4 (anytime during day)
  - HD5: Day 5 (anytime during day)
  - HD6: Day 6 (anytime during day)
  - HD7: Day 7 (anytime during day)
- **If standard care arm do NOT notify the provider of the results**

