## **Training**

All physicians and research staff will undergo in-person training sessions led by the US PI at each site using a standard protocol. Both didactics and proctored bedside scans will occur. This will ensure technique and equipment settings are standardized. Published literature provides strong evidence that LUS can be learned with minimal training: as little as 30 minutes yields excellent correlation with expert sonographers. In addition, established protocols will be utilized for transfer and storage of images.

To ensure ongoing quality assurance, feedback will be provided to each site for every 10 patients, or more frequently as needed if initial review suggests inconsistency. An independent, blinded, expert ultrasonographer will review the images. Concordance with clinical site interpretations will be provided. Additional training will be provided by the

Figure 3: Counting of B-lines using Lung Ultrasound

central reviewer as needed. Inter-rater agreement on B-line counts will be reported at the end of the study.

The CORE lab is led by [name] MD: she is an internationally recognized expert in LUS. She has a proven record of training, both for research and clinical purposes. She has substantial experience in the collation, interpretation, and reporting of LUS images.

**Counting of B-lines:** (Figures courtesy of [name] MD)

B lines will be counted as the number seen per acoustic window. See Figure 3.

In the situation where there is 'white out' or diffuse B lines in a rib space, this will be counted as 10 B-

lines. Half the rib space will be 5. 10 will be the maximum number of B lines per sector.

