### Image Review

All images will be saved as 6-second video clips. Investigators or study staff will label each clip at the time of scan post-enrollment. For example, Scan 0 is at time of enrollment. Scan 24 is 24 hours post-enrollment, Scan 72 is 72 hours post enrollment. All images will also be date/time stamped, which will be recorded in the local site CRF. Investigators or study staff will fill out a table of their count of B-lines, which will be compared to the Core Lab review. If a rib space is completely whited out with B-lines, this will count as 10 B-lines, half the rib space will count as 5. Importantly, the Core Lab will be blinded to the investigator B-line count.

No PHI will be recorded, only a study ID. Each site will separately and securely store linkages from PHI to the study ID per local IRB approved protocols. Currently, all sites have internal processes to store images for quality control as part of their training programs for fellows and residents. Images will then be transferred to a secure, password protected, access limited server with HIPAA grade security.

Local sites will review images to ensure deidentification. Once de-identified, images will be uploaded to a secure, local server with HIPAA grade security. No post-processing will occur. However, prior to upload to the Core Lab, images will be deliberately mixed with other study patients. This is being done to avoid readers from having 'before and after' images. Images will be then uploaded in batches of 5 patients to a secure, HIPAA grade server.

The Core Lab will then download the images. Importantly, the Core Lab will NOT be a study site to minimize any potential bias or failures of de-identification. Furthermore, the Core Lab will not have access to any clinical information on the patient, further limiting the potential for clinical information to bias image interpretation. To minimize the potential bias of having a single sites images reviewed, images from one site will be mixed with other sites upon arrival at the Core Lab. Reviewers will not see images of patients in chronological order or from only one site at a time.

Formal interpretations will be recorded on a standardized, secure CRF accessible only to the Core Lab and the Data Coordinating Center at IU. All investigators will NOT have access to this data until database lock. Applicable back up and secondary storage will occur on a daily basis

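### A fully whited-out sector counts as 20 B-lines in section 17.1 but 10 in section 17.3, so the same scan can fall on either side of the cut-off of 15 used for entry, LUS-arm target and primary endpoint

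*Combined protocol and SAP*

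**What the plan says.** Section 17.1 (Counting B lines) sets these rules:

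- Full white-out: "In the situation where the whole footprint is 'white out' (see below image) count as 20 B lines".
- Half white-out: "If half of the footprint is a 'white out' count as 10 B lines".
- Cap: "The maximum number of B lines per sector is 20".

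Section 17.3 sets different ones:

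- Cap, in the second Training block: "10 will be the maximum number of B lines per sector".
- Full and half white-out, in Image Review: "If a rib space is completely whited out with B-lines, this will count as 10 B-lines, half the rib space will count as 5".

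Both rules feed one score. The Lung Ultrasound Protocol in 17.3 states: "The total number of B-lines for all 8 sectors will comprise the overall score". That total is compared with 15 in three places:

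- section 5.1: more than 15, spread over at least 4 zones, for entry;
- section 4.1: 15 or fewer, as the point at which the LUS-guided protocol stops;
- section 4.2.1: 15 or fewer, as the primary endpoint.

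No section reconciles the two rules or assigns one to the sites and the other to the Core Lab. Section 4.2.1 does not name the reader whose count decides the endpoint.

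**The concern.** The counting rule is part of the definition of the trial's main measurement. Two people who each follow the written plan can score the same clip differently by a factor of two in every white sector. They can then disagree on whether the patient is eligible, whether the LUS-arm target has been met, and whether the primary endpoint has been reached.

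Site staff are exposed to both rules. Section 17.1 trains them and tells them to record counts on the form or in REDCap. The Image Review text in 17.3 states the 10-rule straight after describing their own count table.

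Mixing the rules is worse than using either one throughout. If entry is counted under the 20-rule and the endpoint under the 10-rule, some patients already satisfy the primary endpoint on the T00 eligibility scan. In the reverse case, LUS-guided treatment could stop at a site total of 15 or fewer while the endpoint reader still counts more than 15.

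The planned comparison of readers ("Investigators or study staff will fill out a table of their count of B-lines, which will be compared to the Core Lab review") could also confuse a difference in rule with reader error. The section 10.4.4 analyses of absolute count, relative change and ROC thresholds are affected even in heavily congested scans, because every fully white sector doubles in value from one rule to the other.

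**Working it through.** **Inputs.** Full, half and cap are 20, 10 and 20 in section 17.1, and 10, 5 and 10 in section 17.3. The score is the sum over 8 sectors (17.3). The cut-off is 15 (sections 5.1, 4.1 and 4.2.1).

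**The plan's own sample-size figure.** With 59 per arm, 25% versus 50% and two-sided 0.05, the pooled normal approximation gives z = (0.25 × √59 − 1.96 × √(2 × 0.375 × 0.625)) / √(0.25 × 0.75 + 0.50 × 0.50) = 0.874, so power is 0.809. This matches the stated 81%. Also 118 × 1.10 = 129.8, which matches 130. These figures are not in dispute. Section 10.5 does not say which counting rule lies behind its 25%.

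**Range of the score.** 8 × 20 = 160 under 17.1; 8 × 10 = 80 under 17.3.

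**When the rules disagree.** Let w be the amount of white-out in sector equivalents (full = 1, half = 0.5) and d the number of discrete lines elsewhere.

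- Total under 17.1: 20w + d
- Total under 17.3: 10w + d

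The 17.1 total is never the smaller, so disagreement runs one way only: above 15 under 17.1 and 15 or below under 17.3. The condition is 15 − 20w < d ≤ 15 − 10w.

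| w | white-out adds (17.1) | white-out adds (17.3) | d in conflict |
|---|---|---|---|
| 0.25 | 5 | 2.5 | 11–12 |
| 0.5 | 10 | 5 | 6–10 |
| 0.75 | 15 | 7.5 | 1–7 |
| 1 | 20 | 10 | 0–5 |
| 1.25 | 25 | 12.5 | 0–2 |
| 1.5 | 30 | 15 | 0 |
| 2 | 40 | 20 | none |

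The 0.25, 0.75 and 1.25 rows rest on an assumption. Section 17.1 asks readers to estimate the percentage of white-out, but 17.3 defines only full and half, so its rule is scaled proportionally here.

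**Worked scans.**

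- Entry: one full white-out plus one line in each of three other zones. 20 + 3 = 23, eligible; 10 + 3 = 13, not eligible.
- Entry: one half white-out plus two lines in each of three other zones. 10 + 6 = 16, eligible; 5 + 6 = 11, not eligible.
- Follow-up: one full white-out and nothing else. 20, not resolved; 10, success.
- Two full white-outs: 40 and 20, both above 15.

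The entry examples assume that the involved zones lie on both sides.

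**Scans in conflict at entry.** All 8-zone scans were enumerated with each zone holding 0–6 discrete lines or white-out, and at least 4 zones involved. The limit of 6 lines is a working choice, not a figure from the plan.

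- Half/full grading: w = 0.5 with d = 6–10, or w = 1 with d = 2–5. Totals are 16–25 under 17.1 and 11–15 under 17.3.
- Quarter grading: totals are 16–30 and 8.5–15.

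**Caps alone.** The caps can cause conflict without any white-out. Zones with 13, 1, 1 and 1 lines total 16 under the cap of 20, and 10 + 3 = 13 under the cap of 10. Such scans fall inside the totals above.

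**The other inequality.** Sections 10.2, 10.4.3 and 10.5 write the endpoint as fewer than 15. The conflict then becomes w = 0.5 with d = 5–9 and w = 1 with d = 0–4, and w = 1.5 drops out. The edges move by one line and the conflict remains.

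**The case against.** The strongest reply is that the primary endpoint is protected. Section 4.1 provides for a blinded expert overread, Image Review calls the Core Lab readings the formal ones, and section 17.3, written for that reader, contains only the 10-rule. On that reading 17.1 is site training text, and the endpoint has one scale. This is a fair inference and it narrows the exposure of the endpoint. It does not remove it, because 4.2.1 names no reader. It also leaves entry and LUS-arm decisions on site counts, since of the Core Lab readings the plan says "All investigators will NOT have access to this data until database lock".

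A second reply is that quality control would catch the mismatch. The ultrasound director signs off clips before a scanner enrols patients, the Core Lab reviews 20% of clips, and sites receive concordance feedback every 10 patients with retraining as needed. These checks could shorten the life of a discrepancy, but none is stated to test the white-out rule or the cap, and none says which rule is correct. Training is mainly by video, and neither the video nor the data form can be seen here, so sites may in practice use a single rule.

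Third, eligibility scans precede randomisation. Patients already at 15 or below under the other rule should therefore balance between arms, which would tend to dilute the contrast rather than favour an arm. That stands for entry, but not for LUS-arm decisions made after randomisation.

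Finally, the disagreement is confined to scans near the threshold, and its frequency is unknown. Both points stand and limit what can be claimed about size.

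**Conclusion.** The contradiction is real and must be fixed. Footprint in one section and rib space in the other do not explain it, because each section states its per-sector maximum outright and both rules feed the same 8-sector sum. For scans with white-out worth up to 1.5 sectors and few other lines, the rule alone decides which side of 15 the patient falls on.

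The defect in the text is certain; its effect on results is only potential. The documents do not show that sites count to 20, how often scans fall in the conflict zone, or which rule produced the 25% usual-care rate. No change in event rate or power can therefore be calculated, and its direction is open.

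**What to change.** - Choose one white-out rule and one per-sector cap. The choice is the sponsor's; the documents do not show which was intended. Put identical wording in section 17.1, in both places in 17.3 and on the data collection form, and apply it to site and Core Lab counts alike.
- State in section 4.2.1 and the analysis section that the primary endpoint is the blinded Core Lab 8-sector total under that rule.
- Have the Core Lab re-score stored clips wherever the other rule was used.
- Report by arm how many randomised patients have a Core Lab T00 total of 15 or less. Add a sensitivity analysis of the primary endpoint that leaves them out. The exclusion is defined at baseline, so it does not depend on treatment. Ordinary reader disagreement near 15 will contribute to this group too, so it should be read as a check and not as a count of rule conflicts.

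The cost is revised wording in the manual and analysis plan, some retraining, and re-reading the affected clips. Re-scoring can correct the endpoint. It cannot undo eligibility or LUS-arm treatment decisions already made on site counts, which is the reason to settle the rule early.
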